We propose a two-arm cluster randomized control trial evaluating the feasibility, acceptability, and preliminary impact of ANZANSI (Family economic empowerment + multiple family groups) among 100 adolescent girls and their caregivers. Specifically, this RCT aims to: 1) Refine and pilot test ANZANSI's feasibility and acceptability and its study procedures (recruitment, retention, data collection); 2) Identify barriers and facilitators to ANZANSI's implementation; 3) Estimate intervention parameters (e.g., study population variance, attrition and response rates); and 4) Examine the preliminary impact of ANZANSI (e.g. effect size) on identified outcomes for adolescent girls and their families, post-intervention initiation at 9 months (posttest) and 15 months (6 month follow-up) (see Figure 1).

Figure 1. Anzansi design

Ten schools will be randomly selected from a list of eligible schools, and randomized to one of two study arms: 1) Control arm (n=5 schools, n= 50 adolescent-caregiver dyads): 2) Treatment arm (n=5 schools, n= 50 adolescent-caregiver dyads) receiving ANZANSI (Family economic empowerment + multiple family groups) over a 9-month period. Adolescent girls in the same school will be assigned to the same study condition to avoid contamination.

We hypothesize that following the intervention, compared to the control arm, participants receiving the ANZANSI intervention (treatment arm) will have:

- improved school attendance and attitudes toward schooling;

- b.** lower mean levels of intentions to migrate; and
- c.** improved psychosocial wellbeing, social support and family functioning.

Study setting

The study will be conducted in the Northern region of Ghana, which is one of the three poorest regions in the country, with the highest incidence (81%) of multi-dimensional poverty index, highest rates (35%) of child labor, lowest rates of school attendance in the country. In the region, only 22% of the population age 15 years and older are classified as literate. Specific vulnerabilities relating to young women and girls in the region include traditional gender norms, early and forced marriages, higher rates of school dropout compared to their male counterparts, and being one of the main sending regions for unaccompanied female adolescents to major cities for work.

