Schools within the Tamale District with the highest rates of female student dropouts at the middle school level (based on retrospective 3-year data) will be compiled. Once the list is compiled, the ten schools with the highest female student dropout rates will be selected. Subsequently, schools will be randomly assigned to either control or treatment arm. Following school randomization, the study team will work closely with the schools for recruitment.

Participants

One hundred adolescent girls and their caregivers will participate in the study (n=50 dyads in each arm; 10 per school). Adolescent girls' inclusion criteria are: 1) Enrolled in school and living within a family (defined broadly -not necessarily biological parents); 2) Ages 11 to 14; 3) Capable of giving assent; 4) Skipping school in the past academic term (with at least 10% of unexcused absences). The caregiver inclusion criteria are: 1) Self-identified as primary caregiver of the adolescent girl; and 2) Capable of providing informed consent. Participants (girls and

caregivers) that do not meet the criteria or exhibit a lack of understanding of the study procedures and hence not able to provide informed consent will be excluded.

Recruitment, retention and attrition

School administrators will share a flyer that introduces the project to the students and caregivers; and invite all the caregivers with an eligible child/ren to contact the school for details. The study team will organize meetings with families in each of the selected schools to present the study and answer questions. The research team will then meet with potential participants to engage them in the screening and informed consent process. Adolescent girls will be contacted for assent only after receiving consent from their caregivers. Only families who provide both consent and assent will be recruited to participate in the study.

Study arms

Control arm (Bolstered care). Female adolescents in the bolstered care will receive services/education as usual in their respective schools. The usual care will be bolstered by providing school notebooks and lunch in the control arm (bolstered care will also be provided to treatment arm). Primary school education is universal and free in Ghana. Yet notebooks and lunch are costly expenses for families that create a barrier to school attendance. Hence, these will be provided to participants in all study schools.

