- c. improved psychosocial wellbeing, social support and family functioning.

Children will be the units of analysis for the preliminary analyses. We will plot means by group over time to describe overall patterns of change. We will use linear mixed models (LMMs) to evaluate the proposed hypotheses. We will fit LMMs to ensure that all requisite information is available to perform the types of analyses typically undertaken in a formal RCT of intervention efficacy and to obtain valuable effect size information. LMMs will include random intercepts for school membership and random intercepts and slopes for subjects (three-level models).

Additional exploratory analyses will study caregivers and children jointly as the unit of analysis

via dyadic analysis methods such as actor-partner and means-and-deviation models to quantify caregiver vs. child effects and between- vs. within-dyad effects on psychological wellbeing.

Power calculations. Although the study purpose is to determine preliminary feasibility and acceptability rather than conduct formal hypothesis tests, we conducted several power analyses using NCSS PASS to supply additional information. Our power analyses assume $\alpha=.05$, power=.80, 83 participants retained at the final time point following 17% estimated attrition, and a conservative unconditional intra-class correlation coefficient (ICC) of 9.3% based on our previous SUUBI study of school going children and school attendance in Uganda. For the target enrollment proportion of 70% to assess feasibility, the width to the limit of the confidence interval is 24.4% (standardized distance: .28). For continuous standard normal variables to assess acceptability (e.g., CSQ-8), the distance from the mean to the confidence limit is .26. These distances to confidence limits are between small (.20) and medium (.50) effect sizes. For preliminary efficacy exploratory analyses with two post-baseline time points, minimum detectable standardized mean differences ranged from .56 to .69 for within-subjects correlations ranging from .20 to .80. In sum, our study is powered to detect small to medium distances to confidence limits for descriptive statistics and medium to large longitudinal analysis effects depending on the amount of within-subject correlation of responses, though, as noted previously, hypothesis testing is not the study focus.

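### Ten schools are randomised five to five with no covariate constraint described, although each school's three-year female dropout rate is known before the draw; constrained randomisation would be a cheap gain in balance and possibly in precision

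*Combined protocol and SAP*

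**What the plan says.** The Study setting section ranks middle schools in one district by female dropout, "based on retrospective 3-year data", and states that "the ten schools with the highest female student dropout rates will be selected". The next sentence is all it says about the method of allocation: "Subsequently, schools will be randomly assigned to either control or treatment arm".

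The Methods section fixes the numbers at five schools and 50 dyads per arm, and the Participants section gives "n=50 dyads in each arm; 10 per school". Stratification, pairing, minimisation and constrained randomisation are not mentioned anywhere. Under Preliminary impact, the linear mixed model has random intercepts for school and random intercepts and slopes for subjects. No school-level covariate is named. School attendance is in the first-listed hypothesis.

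The Methods section describes the choice of schools differently: "Ten schools will be randomly selected from a list of eligible schools, and randomized to one of two study arms". That does not agree with taking the ten highest dropout rates.

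**The concern.** Only ten units are randomised, so the arms can easily differ on any school characteristic. One relevant characteristic is in hand before the draw: under the Study setting text, the dropout rate is what brought each school into the trial. It is plausibly related to attendance, although the documents do not call it prognostic. As written, it is used to select schools and then plays no stated part in the allocation or the analysis.

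What is at stake is the usefulness of the preliminary effect sizes, which the protocol wants in order to inform a larger study. If the five schools with the worse dropout histories fall mostly in one arm, readers will doubt the attendance comparison, and the estimate will be noisier than it needs to be.

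**Working it through.** **The plan's own figures.** The documents give no figure for allocation balance. The nearest is the minimum detectable standardised difference of .56 to .69 under Power calculations. With 83 girls, 83/10 = 8.3 per school and ICC .093:

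- Design effect = 1 + 7.3 × .093 = 1.679; effective n = 83/1.679 = 49.4.
- (1.960 + 0.842) × sqrt(4/49.4 × (1 + ρ)/2) gives .62 at ρ = .20 and .76 at ρ = .80.
- The printed .56 to .69 appear if 100 girls replace 83 (100/1.679 = 59.6).

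That difference is a separate matter and does not affect what follows.

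**Step 1: how often the arms differ.** There are C(10,5) = 252 five-versus-five allocations. Standardise the ten dropout rates to SD 1. The arm difference in means then has variance 1/5 + 1/5 = 0.4, so its root mean square is sqrt(0.4) = 0.63 school SD whatever the shape of the rates. The tail frequencies depend on the shape, and the actual rates are not in the documents. Enumerating all 252 allocations over 4,000 simulated sets of normal rates gives:

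| | All 252 | Best-balanced 63 |
|---|---|---|
| More than 0.5 SD apart | 46% | none in a typical set |
| More than 1 SD apart | 12% | none in a typical set |
| Root mean square | 0.63 SD | 0.13 SD |
| Largest difference (average over sets) | – | about 0.22 SD |

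With evenly spaced, normal-score and right-skewed rates, the first two figures run from 42% to 48% and from 10% to 12%. The worst case among the best 63 runs from 0.20 to 0.23 SD.

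**Step 2: what that means on the outcome scale.** With total outcome SD 1, the between-school SD is sqrt(.093) = 0.305. Let r be the school-level correlation between dropout rate and outcome. The documents do not give r; .3 to .9 is an assumed range. The chance contribution to the arm difference has root mean square 0.632 × r × 0.305:

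- r = .3: 0.06 SD
- r = .6: 0.12 SD
- r = .9: 0.17 SD

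Under the constraint, at r = .6, it is 0.13 × 0.6 × 0.305 = 0.02 SD. None of these figures allows for baseline adjustment.

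**Step 3: set it against the standard error.** At one time point, the SE of the arm difference is sqrt(4 × 1.679/83) = 0.284 SD, with variance 0.0809. Suppose the dropout component is removed completely. Adjusting for dropout rate uses one of the 10 − 2 = 8 between-school degrees of freedom. The multiplier t(.975) + t(.80) rises from 2.306 + 0.889 = 3.195 on 8 df to 2.365 + 0.896 = 3.261 on 7 df, a ratio of 1.021.

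| r | Share of variance | SE ratio | × 1.021 | Net gain |
|---|---|---|---|---|
| .3 | 0.0579² / 0.0809 = 4% | 0.979 | 0.999 | about 0% |
| .6 | 0.1157² / 0.0809 = 17% | 0.914 | 0.932 | about 7% |
| .9 | 0.1736² / 0.0809 = 37% | 0.792 | 0.809 | about 19% |

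Net gain is the reduction in the minimum detectable difference.

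**The case against.** A reader might infer that the arm comparison is biased by 0.12 SD or so. The documents do not support that. The draw is random, so the imbalance has mean zero over allocations, and the random school intercept carries between-school variance into the standard error. The cost is in precision and face validity. The intercept does not, however, undo an imbalance that a particular draw has produced.

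A reader might also take the dropout rate as the established key prognostic factor. That is an inference. No section says so, and most outcomes in Table 1, such as self-esteem and family relations, have no stated link to it. The ICC comes from attendance in a Ugandan study. Taking only the ten highest schools in one district, and only girls with at least 10% unexcused absence, may also make the absolute spread small. The percentages in Step 1 are unaffected because they are relative to the SD among the ten, but r could be low, and at .3 the net precision gain vanishes.

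Baseline data weaken the point further. The full battery, including attendance reports, is collected at baseline, and the models are longitudinal, so stable school differences would partly cancel. The plan does not say how baseline enters the model, so how much would remain is unknown. The figures in Steps 2 and 3 are therefore unadjusted.

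It would also be too strong to say that randomisation has no balance constraint or is known to be simple. The five-to-five split is fixed, and the text is silent on any further restriction. What can be said is that no covariate constraint is described.

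Lastly, this is a pilot, and the plan says that hypothesis testing is not its focus. That stands, and it limits the point to the exploratory effect sizes. It does not remove it, because effect-size estimates are among the trial's stated aims.

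**Conclusion.** The point holds as a cheap improvement to the design, not as an error or a threat to validity. With no covariate constraint described, a gap of more than half a school SD in mean dropout rate is close to an even chance (about 46%), and a gap of more than 1 SD occurs in about one allocation in eight (12%). These two figures assume roughly normal rates among the ten schools and change little under other shapes.

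On the outcome scale, the chance component is 0.06 to 0.17 SD within a standard error of about 0.28 SD. Removing it is worth about 0% to 19% of the minimum detectable difference. Those figures rest on the ICC of .093, an assumed correlation of .3 to .9, 83 girls at one time point, and no credit for baseline measures. Enrolment, retention, satisfaction and the qualitative results are unaffected.

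**What to change.** Before the draw, list all 252 five-versus-five allocations and compute the arm difference in mean three-year dropout rate for each. Keep about the best-balanced quarter (about 63), draw one at random, and write the criterion into the protocol. Include dropout rate as a school-level covariate in the arm comparison for the preliminary-impact outcomes; if it is left out, its variance stays in the standard error and the precision gain is not realised. A pair-matched analysis is not needed and would leave only 4 between-school degrees of freedom.

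The cost is a short script and one of the 8 between-school degrees of freedom. If the correlation with outcome is low, there is little or no net gain in precision, and what remains is better face validity. The retained set should not be cut much below 60, so that the draw remains a real randomisation.

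The Methods and Study setting sections should also be reconciled on whether the ten schools are drawn at random from a list or are those with the highest dropout rates. Under either procedure, the rates of the ten chosen schools must be on file before allocation.

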2) CDA. Each participant receives a CDA, a matched savings account held in the adolescent girl's name and her caregiver as a co-signer, in a formal financial institution. Participants' family members, relatives, or friends are allowed and encouraged to contribute towards the CDA. The account is then matched with money from the project. The match cap (the maximum amount of family contribution to be matched by the intervention) is an equivalent of US\$10 per month per family or US\$90 for the 9-months intervention period. SUUBI studies in Kenya and Uganda indicate that families can save these amounts and that the amount is adequate and reinforcing. During the intervention, every equivalent of \$1 saved (in Ghana currency) by the participant and her family, will be matched by \$2 from the project (match rate of 1:2). Thus, female adolescents who save the maximum amount will have \$270 at the end of the intervention (\$90 in their own savings plus \$180 from the match). This money can be used to keep the adolescent girl in school (e.g. pay for school uniform, books, supplies) and/or start a small business for her and her family outside of school hours. During the intervention, each girl, with her primary caregiver as a co-signer, has access to the money in her account (excluding the matching funds). Participants can withdraw their own money (but not the matching funds) only in case of emergency. When ready to use their match for business expenses, participants meet with study team to review their

business plan and supply costs. A check for the matching funds is then written directly to the school or “the vendor,” supplier of the business capital items;

3) Family income-generating activities: Participants are trained on income-generating activities and expected to use part of their matched savings to start an income-generating activity intended to benefit the whole family.

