Upon intervention completion, randomly selected 30 dyads from the treatment arm will participate in interviews about their experiences with the ANZANSI intervention. We expect that this sample size will be sufficient in reaching theoretical saturation. Questions will be translated and back-translated by 2 team members fluent in both English and Dagbani (local language). The interviews will be conducted with caregivers and adolescent girls separately in a private place of their choosing by RAs (trained in qualitative interviewing) using pre-established semi-structured interview protocols. The interviews will focus on: 1) Experiences with the intervention and 2) Key multi-level (individual, family, contextual, and program) influences affecting program participation. Semi-structured interviews elicit richer responses⁷⁴ and will help better understand participants' processes and experiences with ANZANSI; potential processes behind key outcomes and mediating variables; and multi-level factors that may have affected their experiences. Interviews will last 1 hour and will be audio-taped. The interviews will assess intervention feasibility and acceptability, not children's psychosocial functioning. Hence, we do not expect the interviews to influence follow-up assessment.

Data analysis

Quantitative data analysis.

Feasibility. We will monitor recruitment rates and staff level of effort, number of screenings conducted, proportion eligible and agreed to enroll. Enrollment of 70% or higher will be considered feasible. We will also record number of rescheduled, cancelled and missed sessions and assessments to inform estimation of staffing needs and retention protocols for future trials.

Acceptability. We will adapt the Client Satisfaction Questionnaire (CSQ) to assess acceptability. Items include: *“How helpful was ANZANSI in addressing school dropout and intention to migrate to urban centers to work?”* and *“How likely are you to recommend ANZANSI to families whose children are at risk of migrating to urban centers to engage in child labor?”* Given the modest sample size, quantitative analyses of intervention data will be largely descriptive and concentrate on tabulating and summarizing satisfaction outcomes.

Preliminary impact. We expect that following intervention, relative to the control arm, participants in ANZANSI will have:

- a. improved school attendance and attitudes toward schooling;
- b. lower mean levels of intentions to migrate;

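### Families are recruited and consented after their school has been randomised, with no stated concealment, so who enrols may depend on the arm

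*Combined protocol and SAP*

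**What the plan says.** Under Study setting, ten schools are selected and then allocated: "Subsequently, schools will be randomly assigned to either control or treatment arm". The next sentence fixes when recruitment happens: "Following school randomization, the study team will work closely with the schools for recruitment".

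Recruitment, retention and attrition gives the steps. First, "School administrators will share a flyer that introduces the project to the students and caregivers", and all caregivers with an eligible child are invited to get in touch with the school. Then, "The study team will organize meetings with families in each of the selected schools to present the study and answer questions". Screening and caregiver consent follow, then the girl's assent. Participants sets the target at 10 dyads per school and 50 per arm.

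Methods makes the school the unit of allocation: "Adolescent girls in the same school will be assigned to the same study condition to avoid contamination". Both arms receive notebooks and lunch (Study arms). The treatment arm also receives twelve workshops, the multiple family group sessions, and a savings match of two dollars for each dollar saved, worth up to 180 US dollars over nine months (ANZANSI Family Program).

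The feasibility criterion is a single figure, not split by arm: "Enrollment of 70% or higher will be considered feasible". The efficacy model is a linear mixed model with a random intercept for school and random intercepts and slopes for subjects. The text names no group-by-time term and no baseline covariate.

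**The concern.** Randomising schools makes the two sets of schools comparable. It does not make the enrolled families comparable if enrolment happens once the arm can be known. Each school has one arm and its own meeting, so anyone who knows the school's arm knows what each family there would receive. The treatment offer is worth more but asks for saving and for attendance at many sessions, so uptake could be higher or lower than in control. Willingness to join such a programme may well be related to school attitudes, migration intentions and family relations, which are the outcomes.

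The planned methods do not remove such a difference. Intention-to-treat acts only from enrolment onwards, and random effects for school and subject describe correlation, not selection. If baseline is also taken after the arm is known (the order is not stated), baseline self-reports could be affected too.

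What is at stake is the preliminary effect sizes, a stated aim of the pilot and intended to inform a larger study, and the reading of the enrolment criterion. Satisfaction ratings and interviews within the treatment arm are much less exposed.

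**Working it through.** **Order of steps.** Read together, Study setting and Recruitment, retention and attrition give: select schools, randomise, flyer, meetings, screening, consent, assent. The document contains no masking of recruiters, school staff or families, no list of eligible girls drawn up before allocation, and no rule for choosing 10 when more than 10 are willing. The plan gives no figure for possible selection, so there is none to reproduce.

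**Size of a level shift.** From the plan: the smallest stated minimum detectable difference, .56 SD, and the within-subject correlations of .20 to .80 (Power calculations). Assumed: uptake *p* in each arm, and a correlation *ρ* between willingness to enrol and outcome. Treat willingness as standard normal and let the most willing fraction *p* accept. Mean willingness among acceptors is then λ(p) = φ(z)/p, with z the point that a fraction *p* exceeds.

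- λ(.90) = .1755/.90 = .195
- λ(.80) = .2800/.80 = .350
- λ(.70) = .3477/.70 = .497
- λ(.60) = .3863/.60 = .644
- λ(.50) = .3989/.50 = .798

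The shift between arms with no treatment effect is ρ × the difference in λ:

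| Uptake, treatment/control | Difference in λ | Shift, ρ = .1 | Shift, ρ = .5 | ρ = .5 shift as share of .56 |
|---|---|---|---|---|
| 70/70 | 0 | 0 | 0 | 0% |
| 80/70 | .147 | .015 | .073 | 13% |
| 90/60 | .449 | .045 | .224 | 40% |
| 90/50 | .603 | .060 | .301 | 54% |

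The sign depends on which arm has the higher uptake and on the sign of ρ.

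**With a baseline covariate.** Take 90/60 and ρ = .5 with both baseline and follow-up. Selection reduces the variance of willingness by k = λ(λ − z): .195 × (.195 + 1.282) = .288 at 90% and .644 × (.644 + .253) = .578 at 60%, average .433. The within-arm baseline slope is (r − .25 × .433)/(1 − .25 × .433).

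- r = .20: slope (.20 − .108)/.892 = .103; adjusted shift .224 × (1 − .103) = .20 SD
- r = .80: slope (.80 − .108)/.892 = .776; adjusted shift .224 × (1 − .776) = .05 SD

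In a change score, a shift that is the same at baseline and follow-up cancels to 0.

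**Enrolment criterion.** With 50 enrolled per arm and uptake of 90% and 60%, the number approached is 50/.90 + 50/.60 = 55.6 + 83.3 = 138.9. Pooled enrolment is 100/138.9 = 72.0%, which meets 70% although control stands at 60%. A pooled figure does not always hide the gap: 90% and 50% give 100/155.6 = 64%, which fails.

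**The case against.** Disclosure of the arm is inferred. No text says that the flyer or meetings reveal it, and the consent pages are absent from the file, which is not a fault of the plan. This stands as a limit: the order of steps and the silence on concealment are certain, the bias is only possible.

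There are partial safeguards. All caregivers with an eligible child are invited, the absence criterion refers to a past term, both arms get notebooks and lunch, and screening and agreement are counted. These narrow the room for selection by recruiters, but none hides the arm.

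The larger shifts need wide gaps in uptake and a strong correlation; 80/70 gives at most .073 SD. The adjusted .20 SD is also an awkward corner: with ρ = .5 at both times and r = .20, the correlation between baseline and follow-up given willingness is (.20 − .25)/.75 = −.07. If schools fill their places with the keenest 10, and the ranking is the same under both offers, the shift is near zero. These points are fair and are why a range is given.

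Subject slopes and plots of change over time suggest a group-by-time estimate, in which a constant shift cancels. The text does not name that term, however. The stated range .56 to .69 also rises with within-subject correlation roughly as √((1 + r)/2): .56/.69 = .81 against √(1.2/1.8) = .82. That is how a difference in post-baseline means behaves, so comparing a level shift with .56 is reasonable.

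Finally, this is a pilot, and Power calculations says that hypothesis tests are not its focus. That lowers the stakes, but effect sizes and recruitment procedures are both things the pilot sets out to assess.

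**Conclusion.** The concern holds. The plan places recruitment after allocation and states nothing that keeps enrolment independent of the arm. The random allocation of the ten schools is sound; the comparability of the families enrolled within them is unprotected.

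On assumed uptake and correlations, the resulting shift is 0 to 0.30 SD in level, of either sign, or 0 to 54% of the smallest stated detectable difference. It is smaller with baseline adjustment when within-subject correlation is high, and zero in a change score if constant over time. These figures also assume that enrolees are all acceptors or a random draw of them. They show what could happen and do not estimate what will. The point should be fixed because a stated aim depends on it and the remedy is cheap, but it does not undermine the feasibility and acceptability work.

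**What to change.** In all ten schools, identify girls who meet the absence criterion from attendance records, screen them, obtain consent and assent with one form that describes both arms, and complete baseline. Only then generate or reveal the school allocation. Where more than 10 families in a school are eligible and willing, choose 10 at random before allocation. Report the enrolment proportion by arm as well as pooled.

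If the order cannot change, use the same flyer and meeting script in every school, withhold the arm until baseline is complete, and state that effects are estimated as group-by-time or baseline-adjusted.

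The cost is a reordering of steps and a common consent form, with no extra staff or participants. The intervention would start only once baseline is complete in all ten schools, the two ethics approvals may need amending, and some families may be disappointed on learning that their school is in the control arm, which could raise dropout there.
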